#### 5.3.2.3. Solicited symptoms

```
Template Table R - 4
```

Incidence of solicited local symptoms reported during the 7-day (Days 0-6) post-vaccination period

|               |           |                        |                 | [Each group] |   |      |    |  |  |
|---------------|-----------|------------------------|-----------------|--------------|---|------|----|--|--|
|               |           |                        |                 |              |   | 95 % | CI |  |  |
| Symptom       | Follow-up | Туре                   | Ν               | n            | % | LL   | UL |  |  |
|               | (Eac      | h dose)/Overall dose/C | Overall subject |              |   |      |    |  |  |
| Pain          | <= 2 days | All                    |                 |              |   |      |    |  |  |
|               |           | Grade 3                |                 |              |   |      |    |  |  |
|               | > 2 days  | All                    |                 |              |   |      |    |  |  |
|               |           | Grade 3                |                 |              |   |      |    |  |  |
|               | Total     | All                    |                 |              |   |      |    |  |  |
|               |           | Grade 3                |                 |              |   |      |    |  |  |
| Redness (mm)  | <= 2 days | All                    |                 |              |   |      |    |  |  |
|               |           | > 20                   |                 |              |   |      |    |  |  |
|               | > 2 days  | All                    |                 |              |   |      |    |  |  |
|               |           | > 20                   |                 |              |   |      |    |  |  |
|               | Total     | All                    |                 |              |   |      |    |  |  |
|               |           | > 20                   |                 |              |   |      |    |  |  |
| Swelling (mm) | <= 2 days | All                    |                 |              |   |      |    |  |  |
|               |           | > 20                   |                 |              |   |      |    |  |  |
|               | > 2 days  | All                    |                 |              |   |      |    |  |  |
|               |           | > 20                   |                 |              |   |      |    |  |  |
|               | Total     | All                    |                 |              |   |      |    |  |  |
|               |           | > 20                   |                 |              |   |      |    |  |  |

For each dose and overall/subject:

N= number of subjects with at least one documented dose

n/%= number/percentage of subjects reporting at least once the symptom

For Overall/dose:

N= number of documented doses

n/%= number/percentage of doses followed by at least one type of symptom

95%CI= Exact 95% confidence interval; LL = lower limit, UL = upper limit

Data source = Appendix table IIA

| gsk GlaxoSm | nithKline     | Study RAP          |                  |  |  |  |  |  |
|------------------------|---------------|--------------------|------------------|--|--|--|--|--|
| Study Id: 1            | 108706        | Abbreviated Title: | PRO HIV-005      |  |  |  |  |  |
| Version:               | Draft version | ⊠ Final            | Date: 26SEP 2008 |  |  |  |  |  |

Template Table R - 5

Incidence of solicited general symptoms reported during the 7-day (Days 0-6) post-vaccination period

|                |           |             |     | [Each group]                                |   |      |    |  |  |  |
|----------------|-----------|-------------|-----|---|---|------|----|--|--|--|
|                |           |             |     |   |   | 95 % | CI |  |  |  |
| Symptom        | Follow-up | Туре        | Ν   | n   | % | LL   | UL |  |  |  |
|                |           |             | [Ea | [Each dose]/Overall dose/Overall
subject |   |      |    |  |  |  |
| (Each symptom) | <= 2 days | All         |     |   |   |      |    |  |  |  |
|                |           | Grade 3     |     |   |   |      |    |  |  |  |
|                |           | Rel         |     |   |   |      |    |  |  |  |
|                |           | Rel*Grade 3 |     |   |   |      |    |  |  |  |
|                | > 2 days  | All         |     |   |   |      |    |  |  |  |
|                |           | Grade 3     |     |   |   |      |    |  |  |  |
|                |           | Rel         |     |   |   |      |    |  |  |  |
|                |           | Rel*Grade 3 |     |   |   |      |    |  |  |  |
|                | Total     | All         |     |   |   |      |    |  |  |  |
|                |           | Grade 3     |     |   |   |      |    |  |  |  |
|                |           | Rel         |     |   |   |      |    |  |  |  |
|                |           | Rel*Grade 3 |     |   |   |      |    |  |  |  |

For each dose and overall/subject:

N= number of subjects with at least one documented dose

n/%= number/percentage of subjects reporting at least once the symptom

For Overall/dose:

N= number of documented doses

n/%= number/percentage of doses followed by at least one type of symptom

95%CI= Exact 95% confidence interval; LL = lower limit, UL = upper limit

Data source = Appendix table IIB

Template Table R - 6

#### Number of days with symptoms during the solicited postvaccination period

| Solicited symptom | Dose           | Group        | Ν | Mean | Min | Q1 | Median | Q3 | Max |
|-------------------|----------------|--------------|---|------|-----|----|--------|----|-----|
| (Each symptom)    | (Each dose)    | [Each Group] |   |      |     |    |        |    |     |
|                   | [Overall/dose] |              |   |      |     |    |        |    |     |

N = number of doses with the symptom

Q1 = 25th percentile

Q3 = 75th percentile

Data source = Appendix table IIA, Appendix table IIB

| gsk       | SmithKline    | Study RAP          |                  |  |  |  |  |
|-----------|---------------|--------------------|------------------|--|--|--|--|
| Study Id: | 108706        | Abbreviated Title: | PRO HIV-005      |  |  |  |  |
| Version:  | Draft version | ⊠ Final            | Date: 26SEP 2008 |  |  |  |  |

Template Table R - 7

Maximum temperature per dose, overall doses, overall subject (0.5° increments)

|         |  |   | [[ | Each gro | oup] |    |  |  |
|---------|--|---|----|----------|------|----|--|--|
|         |  |   |    |          | 95 % | CI |  |  |
| Symptom | Туре                                     | N | n  | %        | LL   | UL |  |  |
|         | (Each dose)/Overall dose/Overall subject |   |    |          |      |    |  |  |
| Fever   | All                                      |   |    |          |      |    |  |  |
|         | 37.5 - 38.0°C                            |   |    |          |      |    |  |  |
|         | 38.1 - 38.5°C                            |   |    |          |      |    |  |  |
|         | 38.6 - 39.0°C                            |   |    |          |      |    |  |  |
|         | 39.1 - 39.5°C                            |   |    |          |      |    |  |  |
|         | 39.6 - 40.0°C                            |   |    |          |      |    |  |  |
|         | 40.1°C +                                 |   |    |          |      |    |  |  |
|         | Rel*[37.5 - 38.0°C[                      |   |    |          |      |    |  |  |
|         | Rel* [38.1 - 38.5°C[                     |   |    |          |      |    |  |  |
|         | Rel* [38.6 - 39.0°C[                     |   |    |          |      |    |  |  |
|         | Rel* [39.1 - 39.5°C[                     |   |    |          |      |    |  |  |
|         | Rel* [39.6 - 40.0°C[                     |   |    |          |      |    |  |  |
|         | Rel* [40.1°C[                            |   |    |          |      |    |  |  |

For each dose and overall/subject:

N= number of subjects with at least one documented dose

n/%= number/percentage of subjects reporting at least once the symptom For Overall/dose:

N= number of documented doses

n/%= number/percentage of doses followed by at least one type of symptom

95%CI= Exact 95% confidence interval; LL = lower limit, UL = upper limit

Data source = Appendix table IIB

| gsk
GlaxoSmithKline | Study RAP          |                  |  |  |  |
|------------------------|--------------------|------------------|--|--|--|
| Study Id: 108706       | Abbreviated Title: | PRO HIV-005      |  |  |  |
| Version: Draft version | n 🛛 Final          | Date: 26SEP 2008 |  |  |  |
|                        |                    | Date. 203EF 2000 |  |  |  |

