8.5. Evaluating adverse events and serious adverse events

8.5.1. Assessment of intensity

Intensity of the following AEs will be assessed as described:

Table 10 Intensity scales for solicited symptoms

Adverse Event	Intensity grade	Parameter
Pain at injection site	0	Absent
	1	Painful on touch
	2	Painful when limb is moved
	3	Pain that prevents normal activity
Redness at injection site		Record greatest surface diameter in mm
Swelling at injection site		Record greatest surface diameter in mm
Fever*		Record temperature in °C
Headache	0	Normal
	1	Headache that is easily tolerated
	2	Headache that interferes with normal activity
	3	Headache that prevents normal activity
Fatigue	0	Normal
-	1	Fatigue that is easily tolerated
	2	Fatigue that interferes with normal activity
	3	Fatigue that prevents normal activity
Sweating	0	Normal
	1	Sweating that is easily tolerated
	2	Sweating that interferes with normal activity
	3	Sweating that prevents normal activity
Myalgia	0	None
	1	Myalgia that is easily tolerated
	2	Myalgia that interferes with normal activity
	3	Myalgia that prevents normal activity
Gastrointestinal symptoms	0	Gastrointestinal symptoms normal
(nausea, vomiting, diarrhoea and/or abdominal pain)	1	Gastrointestinal symptoms that are easily tolerated
	2	Gastrointestinal symptoms that interfere with normal activity
*F	3	Gastrointestinal symptoms that prevent normal activity

*Fever is defined as axillary or oral temperature \geq 37.5°C.

The maximum intensity of local injection site redness/swelling will be scored at GSK Biologicals as follows:

0	:	0 mm

- 1 : > 0 to ≤ 20 mm
- 2 : $> 20 \text{ to} \le 50 \text{ mm}$
- 3 : > 50 mm

The investigator will make an assessment of the maximum intensity that occurred over the duration of the event for all other AEs, i.e. unsolicited symptoms, including SAEs reported during the study. The assessment will be based on the investigator's clinical judgement. The intensity of each AE and SAE recorded in the Adverse Event screen within the subject's eCRF, SAE screens in the eCRF or SAE Report Form (if back-up reporting system is used) should be assigned to one of the following categories:

1 (mild)	=	An AE which is easily tolerated by the subject, causing minimal discomfort and not interfering with everyday activities.
2 (moderate)	=	An AE which is sufficiently discomforting to interfere with normal everyday activities.

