10.7.3. Analysis of safety

The primary analysis will be based on the Total Vaccinated cohort. If the percent of enrolled subjects excluded from the ATP cohort for analysis is more than 5%, a second analysis based on this ATP cohort will be performed to complement the total analysis.

Adverse events

The following parameters will be tabulated per treatment group:

- The percentage of subjects with at least one local AE (solicited and unsolicited), with at least one general AE (solicited and unsolicited) and with any AE during the solicited follow-up period will be tabulated with exact 95% confidence interval (CI) after each vaccine injection and overall.
- The percentage of vaccine injections followed by at least one local AE (solicited and unsolicited), by at least one general AE (solicited and unsolicited) and by any AE will be tabulated, overall vaccination course, with exact 95% CI.
- The percentage of subjects reporting each individual solicited local and general AE during the solicited follow-up period will be tabulated with exact 95% CI.
- The percentage of vaccine injections followed by each individual solicited local and general AE will be tabulated, overall vaccination course, with exact 95% CI.
- The proportion of subjects with at least one report of unsolicited AE classified by the Medical Dictionary for Regulatory Activities (MedDRA) and reported up to 30 days after vaccination will be tabulated with exact 95% CI.

The same tabulations will be done for grade 3 adverse events and/or for adverse events with relationship to vaccination.

Fever will be reported per 0.5°C cumulative increments.

Serious AEs and withdrawal due to AEs will be described in detail.

Haematological and biochemical parameters

The frequency distribution of values below, within and above normal ranges will be tabulated per treatment group at each scheduled time point.

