## 3.2.5. Solicited symptoms

This analysis will be performed for Month 2 only.

The number and percentage of subjects reporting each individual solicited local and general AE during the solicited follow-up period will be tabulated with exact 95% CI.

The number and percentage of vaccine injections followed by each individual solicited local and general AE will be tabulated, overall vaccination course, with exact 95% CI.

| gsk
GlaxoSmithKline | Stu                | dy RAP           |
|------------------------|--------------------|------------------|
| Study Id: 108706       | Abbreviated Title: | PRO HIV-005      |
| Version: Draft version | ⊠ Final            | Date: 26SEP 2008 |

The maximum intensity of fever and local injection site redness/swelling will be scored as follows:

| Symptoms                       | Grade | Scale             |
|--------------------------------|-------|-------------------|
| Fever                          | 0     | ] 37.5°C          |
| (Oral or Axillary temperature) | 1     | [ 37.5°C – 38°C ] |
| . ,                            | 2     | ] 38°C – 39°C ]   |
|                                | 3     | [ 39°C            |
| Redness/Swelling               | 0     | 0 mmm             |
|                                | 1     | [ 20 mm           |
|                                | 2     | ]20 mm – 50 mm ]  |
|                                | 3     | ] 50 mm           |

The same tabulations will be done for grade 3 adverse events and/or for adverse events with relationship to vaccination.

The number and percentage of of subjects reporting a solicited symptom will be also presented by duration ( $\leq 2$  days or > 2 days).

For fever, temperatures will be also summarized in 0.5°C increments.

The number of days with a solicited symptom during the solicited follow-up period will be aslo presented. The same tabulations will be done for grade 3 adverse events and/or for adverse events with relationship to vaccination.

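### Fever of exactly 39.0°C is both Grade 2 and Grade 3 in SAP 3.2.5, and the related-fever bands of Template Table R-7 leave out their own upper limits

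*SAP*

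**What the plan says.** The protocol defines fever as 37.5°C or above but gives it no intensity grades. Table 10 (section 8.5.1) says only "Record temperature in °C". For reporting, Protocol 10.7.3 says "Fever will be reported per 0.5°C cumulative increments" and lists no thresholds.

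SAP 3.2.5 supplies the grades. In ordinary interval notation its main scale reads: Grade 0 below 37.5, Grade 1 [37.5, 38], Grade 2 (38, 39], Grade 3 [39, ∞). It then adds "For fever, temperatures will be also summarized in 0.5°C increments", without the protocol's word cumulative.

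Template Table R-7 (SAP 5.3.2.3) carries out that summary. It has an All row, six unrestricted bands from 37.5–38.0 to 40.1 and above, and six bands restricted to related fever. The first five related bands are "Rel*[37.5 - 38.0°C", "Rel* [38.1 - 38.5°C", "Rel* [38.6 - 39.0°C", "Rel* [39.1 - 39.5°C" and "Rel* [39.6 - 40.0°C". Each of these is followed in the template by an outward-facing bracket, so the upper limit is open. The unrestricted bands carry the same numbers with no brackets.

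SAP 3.2.10 has a second, exploratory fever scale, in which Grade 2 is [38.5, 39) and Grade 3 is [39, 40). SAP section 4, which lists changes from the protocol, does not mention fever.

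**The concern.** Occurrence, intensity and relationship to vaccination of solicited symptoms are primary endpoints (Protocol 10.1, SAP 2.2.1), and SAP 3.2.5 is the only definition of Grade 3 fever on the main scale. If 39.0°C belongs to two grades, the Grade 3 count depends on which condition the program tests first. The tables affected are R-5 (fever, Grade 3 and related Grade 3), R-6.2 and R-6.4 (days with Grade 3 and with related Grade 3 symptoms), and R-3.2 and R-3.4 (any Grade 3 symptom, where a subject's only such symptom is a 39.0°C fever).

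In R-7 the fault is different. A program that follows the printed bounds would under-count related fever by band, and the related bands would not add up to the related-fever total in R-5. The shortfall would come from punctuation alone.

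**Working it through.** **1. What the brackets mean.** The grade table uses one-sided entries, so I checked the convention against entries whose meaning is fixed elsewhere:

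- Grade 0 fever, `]` before 37.5: excluded, because Grade 1 starts at 37.5.
- Grade 1 redness/swelling, `[` before 20 mm: included (Protocol 8.5.1: up to and including 20 mm).
- Grade 3 redness/swelling, `]` before 50 mm: excluded (Protocol 8.5.1: above 50 mm).
- Exploratory Grade 0 fever, `]` before 38: excluded, because Grade 1 starts at 38.
- Exploratory Grade 4 fever, `[` before 40: included, because Grade 3 stops short of 40.
- Exploratory Grade 3 redness/swelling, `]` before 100 mm: excluded, because Grade 2 includes 100 mm.

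All six agree: `[` includes the number and `]` excludes it. Main-scale Grade 3 fever is printed with `[` before 39, so it includes 39.0. Grade 2 also includes 39.0.

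**2. Coverage.** I assigned each value in 0.1°C steps to every category that contains it, from 37.0 to 41.0 for the grade scales and from 37.5 to 41.0 for R-7. The 0.1°C resolution is an assumption taken from the printed bounds.

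| Scale | In two categories | In no category |
|---|---|---|
| SAP 3.2.5 as printed | 39.0 | none |
| SAP 3.2.5 with Grade 3 open at 39 | none | none |
| SAP 3.2.10 exploratory | none | none |
| R-7 unrestricted bands | none | none |
| R-7 related bands as printed | none | 38.0, 38.5, 39.0, 39.5, 40.0 |
| R-7 related bands if closed | none | none |

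For example, a related fever peaking at 38.5°C is excluded from the second related band by its open upper limit and from the third because that band starts at 38.6.

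**3. Whether another table settles 39.0°C.** R-7 puts 39.0 at the top of its 38.6–39.0 band and starts the next at 39.1, which suits Grade 3 above 39.0. The exploratory scale puts 39.0 in Grade 3, which suits Grade 3 from 39.0. If the main scale includes 39.0 in Grade 3, its counts cannot be rebuilt from R-7. If it excludes 39.0, it departs from the exploratory scale. The documents do not choose.

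**4. Size of one reclassification.** With planned group sizes of 50 (AS01B) and 10 (WFI), one subject is 1/50 = 2 percentage points or 1/10 = 10 percentage points.

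**The case against.** The strongest reply is that both faults are slips of notation. The related bands repeat the numbers of the closed unrestricted bands, each starting 0.1°C above the one before. That step makes sense only with closed limits, and the last related band even puts brackets around a single number. The 39.0°C overlap rests on one bracket in a table read from PDF. R-7 is a supplementary summary, Table R-5 reports related fever without temperature bands, and Appendix Table II.B lists individual general symptoms. Solicited symptoms are analysed at Month 2 only, and SAP 2.5 says that analysis has already been performed, so the program may well have used sensible bounds.

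Much of this stands. The related brackets probably are a slip, and R-5 would expose any shortfall in R-7. An extraction error is unlikely to explain the overlap, since all six one-sided entries that can be checked follow the same convention, but the source PDF should be consulted. None of this says which grade 39.0°C belongs to, and the SAP remains the text against which the program is verified. The clinical report is written at study completion (Protocol 10.8, SAP 2.5), so a check is still useful.

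**Conclusion.** Two limited errors hold as written. On the main scale, 39.0°C is in both Grade 2 and Grade 3, so Grade 3 fever is not uniquely defined; each affected subject shifts a rate by 2 points (n=50) or 10 points (n=10). In R-7, related fevers peaking at exactly five temperatures have no related band. Both conclusions assume the brackets are reproduced correctly from the PDF; the second also assumes recording to 0.1°C. The change from cumulative increments to separate bands is also missing from SAP section 4.

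A reader might infer more, without support from the documents:

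- That these fevers vanish from R-7. They do not: each is in All and in an unrestricted band, and the related ones are in the R-5 related row.
- That the fever categories are faulty throughout. The exploratory scale and the unrestricted R-7 bands are sound; the main scale overlaps but has no gap, and the related bands have gaps but no overlap.
- That 5 missing values out of the 26 from 37.5 to 40.0°C means 19% of related fevers are lost. That is a share of possible readings. No temperature distribution is given, so neither the number of events affected nor a greater loss in groups with more fever can be derived.
- That the protocol prescribes particular cumulative cut-points. It names only the 0.5°C step.

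**What to change.** 1. In SAP 3.2.5, make Grades 2 and 3 mutually exclusive at 39.0°C. The side is the sponsor's choice, but it should be reconciled with R-7 (split at 39.0/39.1) and with SAP 3.2.10 (39.0 in Grade 3), and any remaining difference should be stated.
2. In Template Table R-7, give the related bands the same closed bounds as the unrestricted bands.
3. Check which bounds the Month 2 program applied. If they differ from the corrected text, re-run or footnote R-3.2, R-3.4, R-5, R-6.2, R-6.4 and R-7 as needed.
4. Add to SAP section 4 that separate 0.5°C bands replace the protocol's cumulative increments.

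The cost is a few lines of SAP text, one program check and possibly a re-run of existing tables. No new data and no change in study procedures are needed.

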#### 5.3.2.4. Unsolicited symptoms

 Template Table R - 8
 Percentage of subjects reporting the occurrence of unsolicited symptoms classified by MedDRA Primary System Organ Class and Preferred Term within the 30-day (Days 0-29) post-vaccination period

| System               | Preferred             |   | [Each group] (N=) |       |    |  |  |  |
|----------------------|-----------------------|---|-------------------|-------|----|--|--|--|
| Organ Class          | Term                  | n | %                 | 95%CI |    |  |  |  |
| (CODE)               | (CODE)                |   |                   | LL    | UL |  |  |  |
| At least one symptom |                       |   |                   |       |    |  |  |  |
| [Each SOC]           | [Each preferred term] |   |                   |       |    |  |  |  |
|                      |                       |   |                   |       |    |  |  |  |
|                      |                       |   |                   |       |    |  |  |  |
|                      |                       |   |                   |       |    |  |  |  |

At least one symptom = at least one symptom experienced (regardless of the MedDRA Preferred Term) N = number of administered doses

n/% = number/percentage of doses with the symptom

95% CI= exact 95% confidence interval; LL = Lower Limit, UL = Upper Limit

Data source = Appendix table IICi

| gsk       | SmithKline    | Study RAP          |                  |  |  |  |
|-----------|---------------|--------------------|------------------|--|--|--|
| Study Id: | 108706        | Abbreviated Title: | PRO HIV-005      |  |  |  |
| Version:  | Draft version | ⊠ Final            | Date: 26SEP 2008 |  |  |  |

Template Table R - 9

Percentage of doses with unsolicited symptoms classified by MedDRA Primary System Organ Class and Preferred Term, within the 30-day (Days 0-29) post-vaccination period

| System               |                       | [Each group] (N=) |   |       |    |  |  |
|----------------------|-----------------------|-------------------|---|-------|----|--|--|
| Organ Class          | Term                  | n                 | % | 95%CI |    |  |  |
| (CODE)               | (CODE)                |                   |   | LL    | UL |  |  |
| At least one symptom |                       |                   |   |       |    |  |  |
| [Each SOC]           | [Each preferred term] |                   |   |       |    |  |  |
|                      |                       |                   |   |       |    |  |  |
|                      |                       |                   |   |       |    |  |  |
|                      |                       |                   |   |       |    |  |  |

At least one symptom = at least one symptom experienced (regardless of the MedDRA Preferred Term) N = number of administered doses

n/% = number/percentage of doses with the symptom

95% CI= exact 95% confidence interval; LL = Lower Limit, UL = Upper Limit

Data source = Appendix table IICi

#### Template Table R - 10

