## 2.2. Endpoints

## 2.2.1. Primary endpoints

## Reactogenicity and safety

- Occurrence, intensity and relationship to vaccination of solicited local and general symptoms during a 7-day (Day 0 to Day 6) follow-up period after each vaccination.
- Occurrence, intensity and relationship to vaccination of unsolicited symptoms during a 30-day (Day 0 to Day 29) follow-up period after each vaccination.

| gsk
GlaxoSmithKline | Stu                | dy RAP           |
|------------------------|--------------------|------------------|
| Study Id: 108706       | Abbreviated Title: | PRO HIV-005      |
| Version: Draft version | ⊠ Final            | Date: 26SEP 2008 |

- Occurrence and relationship to vaccination of serious adverse events during the whole study period.
- Haematological and biochemical levels at months 0, 1, 2, 6, 9, 12 and at Day 44 (two weeks after the second vaccination) in all subjects.

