## 3.2.2. Handling of missing data

For the analysis of solicited symptoms, missing or non-evaluable measurements will not be replaced. Therefore the analysis of the solicited symptoms based on the

| gsk
GlaxoSmithKline | Study RAP          |                  |
|------------------------|--------------------|------------------|
| Study Id: 108706       | Abbreviated Title: | PRO HIV-005      |
| Version: Draft version | on 🛛 Final         | Date: 26SEP 2008 |

totalvaccinated cohort will include only subjects/doses with documented safety data (i.e.symptom screen/sheet completed).

For the analysis of unsolicited adverse events/serious adverse event/concomitant medication, all vaccinated subjects will be considered and subjects who did not report an event will be considered as subjects without an event.

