## 3.2.6. Unsolicited symptoms

This analysis will be performed for Month 2 only.

The proportion of subjects with at least one report of unsolicited AE classified by the Medical Dictionary for Regulatory Activities (MedDRA) and reported up to 30 days after vaccination will be tabulated with exact 95% CI.

The same tabulations will be done for grade 3 adverse events and/or for adverse events with relationship to vaccination.

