#### Minimum and maximum activity dates

| Activity number |              | Minimum date | Maximum date |
|-----------------|--------------|--------------|--------------|
| [Each activity] | [Each visit] | DDMMMYYYY    | DDMMMYYYY    |
|                 |              | DDMMMYYYY    | DDMMMYYYY    |

| gsk
GlaxoSmithKline | Stu                | dy RAP           |
|------------------------|--------------------|------------------|
| Study Id: 108706       | Abbreviated Title: | PRO HIV-005      |
| Version: Draft version | ⊠ Final            | Date: 26SEP 2008 |
|                        | CONFIDENTIAL       |                  |

Template Table D - 5

Number and percentage of subjects who received the vaccine dose(s)

|     | [Each group]
(N =) |   | To
(N | ital
  =) |
|-----|-----------------------|---|----------|--------------|
|     | n                     | % | n        | %            |
| 1   |                       |   |          |              |
| 2   |                       |   |          |              |
| Any |                       |   |          |              |

N = number of subjects in each group or in total included in the considered cohort

n/% = number/percentage of subjects receiving the specified total number of doses in each group or in total

Any = number and percentage of subjects receiving at least one dose

Data source = Appendix table IG, Appendix table IIA, Appendix table IIB

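### Template R-8 defines its per-subject unsolicited-symptom percentages on doses, and Template R-4 has no grade 3 row for redness or swelling

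*SAP*

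**What the plan says.** **Unsolicited symptoms.** SAP 2.2.1 makes this a primary endpoint: "Occurrence, intensity and relationship to vaccination of unsolicited symptoms during a 30-day (Day 0 to Day 29) follow-up period after each vaccination". SAP 3.2.6 plans "The proportion of subjects with at least one report of unsolicited AE", and protocol 10.7.3 plans the same quantity: "The proportion of subjects with at least one report of unsolicited AE classified by the". SAP 3.2.2 fixes the denominator: "all vaccinated subjects will be considered and subjects who did not report an event" count as subjects without an event.

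Template R-8 (SAP 5.3.2.4) is titled "Percentage of subjects reporting the occurrence of unsolicited symptoms classified by MedDRA Primary System Organ Class and Preferred Term". Its footnote says "N = number of administered doses" and "n/% = number/percentage of doses with the symptom". Template R-9, the per-dose table, carries the same two lines word for word. The list of tables in SAP 5.2 assigns R-8 to Tables R-8.1 (all), R-9.1 (grade 3) and R-10.1 (related), all named as percentages of subjects. It assigns R-9 to the per-dose Tables R-8.2, R-9.2 and R-10.2.

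**Redness and swelling.** SAP 3.2.5 plans the incidence of each solicited symptom by subject and by injection with exact intervals, and then the same for grade 3. It scores redness and swelling above 50 mm as grade 3, as does protocol 8.5.1. Template R-4 (SAP 5.3.2.3) has a grade 3 row for pain. For redness and swelling it has only an all-sizes row and a row above 20 mm.

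**The concern.** The footnote is the only place where Template R-8 defines N, n and %. A programmer who follows it, or a reader who uses it to interpret the output, gets a dose rate under a subject title. The three tables would then repeat R-8.2, R-9.2 and R-10.2. No listed table would give subject incidence by System Organ Class and Preferred Term, because Template R-10 supplies only an overall subject count without a percentage or interval. SAP 2.5 reports that the Month 2 analysis has been performed, so existing output needs checking as well as the footnote.

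In Template R-4 the row above 20 mm pools grades 2 and 3, so it cannot stand in for grade 3. Intensity of solicited symptoms is also a primary endpoint.

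**Working it through.** The documents state no figure on this point, so there is nothing to reproduce first.

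**Inputs.** Two vaccinations per subject (SAP 2.1.2). Groups of 50 adjuvanted and 10 non-adjuvanted subjects (protocol 4.1). Exact Clopper-Pearson two-sided 95% intervals (SAP 3.4). The event counts below are assumed.

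**Template R-8: ratio.** Let n be the number of subjects, s those with the symptom at least once, b those with it after both doses, and D the doses given.

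- Subject percentage: s/n.
- Percentage under the literal footnote: (s + b)/D.
- Ratio: (1 + b/s) × n/D.

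With everyone given both doses, D = 2n and the ratio is (1 + b/s)/2. It runs from 0.5 (b = 0) to 1.0 (b = s). If some subjects miss dose 2, D is below 2n and both limits rise.

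**Template R-8: example.** With n = 50, s = 20, D = 100, the subject result is 20/50 = 40.0% (26.4 to 54.8).

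| Affected after both doses | Literal footnote | Exact 95% CI |
|---|---|---|
| none (b = 0) | 20/100 = 20.0% | 12.7 to 29.2 |
| half (b = 10) | 30/100 = 30.0% | 21.2 to 40.0 |
| all (b = 20) | 40/100 = 40.0% | 30.3 to 50.3 |

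In the last row the percentage is right but the interval is not. Its width is 50.3 − 30.3 = 20.0 points, against 54.8 − 26.4 = 28.4 by subject, a ratio of 0.70. Two doses in one person are being counted as independent.

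With no events the upper limit is 1 − 0.025^(1/N). For N = 50 it is 7.1% and for N = 100 it is 3.6%. For N = 10 it is 30.8% and for N = 20 it is 16.8%.

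**Would a check on the numerators find the error?** Suppose the R-8.1 numerator is compared with the subject count in R-8.3. With b = 0, 20 doses match 20 subjects and the check passes. With no events, 0 matches 0. Only the header N shows the error, 100 against 50. The header check needs the vaccinated-subject count from Template D-5: "Any = number and percentage of subjects receiving at least one dose".

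**Template R-4: what other listed tables supply.**

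- Table R-6.2 gives the number of doses with each grade 3 symptom, by dose and group. A per-dose rate can be worked out by hand, but not a per-subject one.
- Table R-3.2 gives grade 3 local symptoms per dose and overall per subject with exact intervals, but pools pain, redness, swelling and unsolicited local symptoms.
- SAP 3.2.10 plans a regrading with cut points at 50 and 100 mm. Its grades 2 and 3 together equal above 50 mm, but its grade 3 is above 100 mm, and SAP 5.2 assigns no table to it.

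Suppose R-6.2 shows 3 grade 3 redness reactions after each dose in a group of 50. The per-dose rate is 3/50 = 6.0% (1.3 to 16.5). If the same subjects reacted both times, the per-subject figure is also 3/50 = 6.0% (1.3 to 16.5). If they were different subjects, it is 6/50 = 12.0% (4.5 to 24.3). The overall per-subject local count in R-3.2 caps this: a count of 3 fixes redness at 3/50, whereas a count of 6 or more leaves the whole range open. The per-subject row above 20 mm in R-4 is a further cap.

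**The case against.** **On R-8**, the strongest reply is that the rest of the plan settles the unit. The template's title, the names of the three tables, SAP 3.2.2, SAP 3.2.6 and protocol 10.7.3 all point to subjects. The literal reading would print one set of tables twice under different titles, so a competent programmer would probably not adopt it. The numerical examples use assumed counts, and halving is the extreme case. All of this stands and limits the weight of the point. It does not make the footnote harmless: a stated definition of N and % for a primary endpoint is wrong, and the version dated 26 September 2008 still carries it after the Month 2 analysis.

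A reader might infer that the Month 2 unsolicited-symptom results were computed on doses and are understated. The documents do not support that. They contain no output, and every statement outside the footnote says subjects.

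**On R-4**, the reply is that grade 3 local reactions are reported elsewhere, that the sizes are in listing II.A, and that no holding rule in protocol 5.6.3 turns on grade 3 redness or swelling. This too stands in part. A reader might infer that the per-subject grade 3 figure is always ambiguous across the full range. That goes too far, because R-3.2 bounds it and sometimes fixes it. Nor does SAP 3.2.5 expressly promise grade 3 by duration: its first grade 3 sentence precedes the duration sentence, and the second follows the number-of-days tabulation, which R-6.2 delivers. The duration split for grade 3 appears only in the template's pain rows. What remains is that a planned per-symptom incidence with its interval has no row.

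**Conclusion.** Both defects are in the text and should be corrected. Template R-8 carries a per-dose footnote, probably copied from R-9, on three per-subject tables. If it were followed with both doses given to everyone, the percentages would be 0.5 to 1.0 times the subject incidence and the exact intervals too narrow. Whether that happened cannot be told from the documents.

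Template R-4 omits the grade 3 row that SAP 3.2.5 calls for in redness and swelling. No listed table gives the per-symptom, per-subject grade 3 percentage with its exact interval. The 6% to 12% range is an upper bound on the ambiguity in one example, which R-3.2 may narrow.

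The sizes rest on assumed event counts and full two-dose compliance. Neither defect shows that a reported result is wrong.

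**What to change.** **Template R-8.** Define N as subjects given one or more doses, and n and % as subjects who reported the symptom at least once. Templates R-14 and R-4 already hold suitable subject-level wording. Then check Month 2 Tables R-8.1, R-9.1 and R-10.1 in two steps:

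1. The header N of each group equals the 'Any' count in Table D.9-5.
2. The n for at least one symptom equals the subject count in R-8.3, R-9.3 and R-10.3 respectively.

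Both steps are needed. Re-run only the tables that fail. The cost is two footnote lines and a check of three tables.

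**Template R-4.** Add a row above 50 mm, marked grade 3, for redness and for swelling. Label the row above 20 mm as grade 2 or 3. Run this as an added tabulation on the Month 2 data. In the total rows alone it adds 2 rows in each of four blocks (dose 1, dose 2, overall per dose, overall per subject), or 8 rows. Adding both duration categories, to match pain, makes 3 × 2 = 6 rows per block, or 24. That extension is for consistency and is optional. No new data are needed, since the sizes are in listing II.A.
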